9. STATISTICAL CONSIDERATIONS

C3FIT will compare the effectiveness of the JC-certified CSC/PSC care system with the ISPU care system in improving patient outcome and quality of life post-stroke. The primary outcome is the SIS-3.0 at 12 months, while assessment at 3 and 6 months are part of secondary outcomes. The primary analysis will focus on intervention differences in mean SIS score at 12 months. Mixed models will be used to assess the SIS outcome at 12 months, allowing the hierarchical nature of the data to be reflected (patients within Sites), and providing an accounting for data that are not missing completely at random. We anticipate (and trust) that randomization will balance potential confounding factors; however, secondary analysis will be performed with adjustment for baseline factors that could be imbalanced and potentially confound the estimated intervention differences, specifically adjusting for factors assessed at baseline that are known to be strongly associated with stroke outcomes (specifically age and stroke severity). Patients who die or cannot return due to morbid conditions will be assigned to “floor” score for poor outcome (and hence does not reduce the number of evaluable patients). With these patients not representing missing data, we anticipate there will be relatively little additional missing data and that these data will be generally missing at random (i.e., patients not returning because of other conditions, like moving); however, missing data that is present will be addressed by including baseline, 3, and 6 month data in the model and allowing the mixed model to adjust estimates for the missing data at 12 months by incorporating information available through the correlation between measurements.

A. Sample Size

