## **1. Introduction**

C3FIT is a cluster -randomized clinical trial randomizing 24 sites (21 of which provided data and will be included) to assess the effectiveness, defined at 12-months post-stroke discharge, of post-stroke care delivered using the Joint Commission (JC)-certified Comprehensive or Primary Care (CSC/PSC) model compared to an integrated, coordinated, technology-enabled Integrated Stroke Practice Unit (ISPU) model (that includes CSC/PSC care). The trial has two primary outcomes, the modified Rankin score (mRS) and the Stroke Impact Scale (SIS), both assessed at baseline (for SIS, only in approximately 50% of the participants), and at 3, 6 and 12 months. Any beneficial treatment effect of the ISPU approach on the mRS and SIS is presumed to be through a beneficial effect on “intermediate” factors, specifically better control of: 1) systolic blood pressure (SBP) to levels below 130 mmHg, 2) LDL levels to levels below 70 mg/dL, 3) HbA1c to levels below 7%, 4) smoking cessation, 5) adherence to AHA diet guidelines by following a Mediterranean-type or DASH diet, and 6) adherence to AHA exercise guidelines by a usual exercise level of moderate or above. Each of these intermediate factors will be assessed among those failing to be in control at hospital discharge (i.e., for SBP, among those with discharge SBP $\geq$ 130 mmHg; for LDL, among those with discharge LDL levels above 70 mg/dL, etc.). Because of this presumed pathway for potential effects, the assessment of treatment effects on these six intermediate factors is considered an integral part of the assessment of primary outcomes. Because the cluster-randomization may fail to balance the treatment groups on key factors potentially affecting outcome, treatment differences will be assessed after a series of incremental models, first in a crude model with no adjustment, then with adjustment for measures of stroke severity, then with further adjustment for demographic factors, and then with further adjustment for major cardiovascular risk factors. Treatment differences for both the two primary outcome variables and the six intermediate factors will be assessed using a mixed model approach including the assessments at baseline, 3 months, 6 months and 12 months.

Beyond the intermediate factors above, the study also has secondary outcomes including mortality, recurrent stroke, rehospitalization, time at home, depression, caregiver strain, and perceived support.

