## **2. Definitions and classification of covariates**

The covariates used in the incremental models include measures of stroke severity, demographic factors, and traditional cerebrovascular risk factors.

- Measures of stroke severity
  - Discharge location, classified as discharged home vs. not home (skilled nursing, rehabilitation center, etc.).

- Discharge mRS, categorized as 0, 1, 2, 3 or 4 or more (noting relatively few patients with discharge mRS of 5).
- Discharge NIH Stroke Scale (NIHSS), categorized into approximate quartiles of 0, 1, 2-4 or 5+
- Stroke subtype (hemorrhage vs. infarction)
- Demographic factors
  - Age, considered as a continuous factor
  - Male sex
  - Race/Ethnicity, categorized as non-Hispanic white (NHW) versus not NHW (including both other races and Hispanic participants)
  - A summary neighborhood index of socio-economic status (nSES) based on previously published methods, including six variables representing wealth/income, education and occupation: (1) log of median household income, (2) log of median value of owner-occupied housing units, (3) proportion of households receiving interest, dividend, or net rental income, (4) proportion of adults aged  $\geq 25$  years with a high school diploma, (5) proportion of adults aged  $\geq 25$  years with college degree, and (6) proportion of people employed in executive, managerial or professional occupations.
- Baseline cerebrovascular risk factors
  - Cigarette smoking, categorized as current vs. non-current (past or never)
  - Hypertension as a dichotomous variable
  - Dyslipidemia as a dichotomous variable
  - Diabetes as a dichotomous variable
  - Atrial fibrillation or irregular heartbeat as a dichotomous variable
  - Sedentary activity (defined as a score of 0-No Physical Activity or 1-Sedentary or sitting most of the time)

Because the mixed models will include baseline assessment of the outcome variable (i.e., outcomes include measures at times 0, 3, 6, and 12 months), covariates directly related to the outcome being assessed will be excluded from the model. That is, variables will not be used as both an outcome and as a predictor in the same model. For example, discharge mRS will not be included in the models predicting treatment differences in mRS, and baseline hypertension will not be included in models assessing treatment differences in SBP. Rather, changes from baseline to the 3, 6 and 12-month visits will be assessed using contrast statements.

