### **3. Primary Outcome Analyses**

#### **3.1. Analysis of intermediate factors**

Because the ISPU intervention was targeted to specific groups determined by baseline assessments, the primary analysis of the six intermediate factors will be restricted to the estimation of treatment differences among patients who were not in control at discharge, specifically assessing the percentage of patients with:

- 1) SBP below 130 mmHg at 3, 6, and 12-months among those with SBP of 130 mmHg or above at discharge
- 2) LDL below 70 mg/dL at 3, 6, and 12-months among those with LDL of 70 mg/dL or above at discharge

- 3) HbA1c below 7% at 3, 6, and 12 months among those with HbA1c of 7% or above at discharge
- 4) Smoking cessation at 3, 6, and 12-months among those smoking at dischargement,
- 5) Adhering to a Mediterranean or DASH diet among those not adhering at baseline
- 6) Having regular exercise levels of moderate or above among those with lower levels at baseline.

The primary hypothesis will focus on compliance/adherence at the 12-month visit, but mixed models will be used with assessments at the 3 time points (3, 6, and 12 months) and treatment differences reported at all three follow-up times.

Analyses will generally take the approach of using a mixed model approach with: 1) repeated measures at 3, 6 and 12 months, and 2) a random effect for patient and site (if models do not converge, site will be considered as affixed effect). As all of the intermediate factors will be dichotomized for the follow-up assessments, outcomes will be assessed using PROC GLIMMIX. Treatment differences will be assessed in a series of incremental models: 1) crude, 2) adjusted for stroke severity, 3) further adjustment for demographics, and 4) adjustment for cerebrovascular risk factors (see section 2 for factors in each group). The temporal pattern of treatment differences at 3, 6 and 12-months will be described by the treatment-specific proportion adherent/compliant with 95% confidence intervals. The primary assessment of treatment efficacy will be the p-value and confidence intervals for the treatment difference in the proportion at the 12th months; however, p-values and confidence intervals for months 3 and 6 will also be reported.

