### **3.3. Stroke Impact Scale (SIS)**

The SIS is a continuous outcome variable with a range from 0 to 100 which will be analyzed identically to continuous intervening factors measured at 4 timepoints (including the analysis with inverse probability weighting). We do note that: 1) after approximately half the patients were recruited, a decision was made to not collect SIS at baseline; however, it is quite reasonable to assume that this decision will give rise to data missing at random and the missingness will be addressed by the mixed models, and 2) the baseline SIS collected were the “long form” of the questionnaire (96 items); however, the 16 items in the short form used at 3, 6 and 12 months are a subset of the long form, and these items will be extracted and scored identically with the follow-up assessments. The analysis of SIS will employ analysis for a continuous factor, but will follow the modeling approach described above for mRS, specifically reporting treatment differences in mean SIS rather than treatment differences in the proportion with good mRS outcome (primary outcome as treatment difference in the change in mean SIS between baseline and 12 months, 4-level incremental models, with/without inverse probability weighting, assessment of effect modifiers, etc.).

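### SAP 3.3 names no within-patient covariance beyond a patient random effect; with a random intercept alone, the standard error of the primary SIS change can be too small

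*SAP*

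**What the plan says.** SAP 3.1 describes the general approach as "using a mixed model approach with: 1) repeated measures at 3, 6 and 12 months", and then, as a second item, "a random effect for patient and site (if models do not converge, site will be considered as affixed effect". It is written for the six dichotomised intermediate factors at three follow-up visits.

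SAP 3.3 says that SIS "will be analyzed identically to continuous intervening factors measured at 4 timepoints" and that its analysis "will follow the modeling approach described above for mRS". The primary SIS result is given as "primary outcome as treatment difference in the change in mean SIS between baseline and 12 months". SAP 2 adds that "changes from baseline to the 3, 6 and 12-month visits will be assessed using contrast statements", so the primary test is a contrast of visit means from one joint model of months 0, 3, 6 and 12.

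The SAP names no residual covariance structure, robust standard error or degrees-of-freedom method. SAP 1 reports that SIS was measured at baseline "for SIS, only in approximately 50% of the participants". Protocol 9 relies on the mixed model "incorporating information available through the correlation between measurements" to deal with missing month-12 data, but neither document gives a between-visit correlation for SIS or an SD by visit.

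**The concern.** A patient random intercept with independent residuals makes every pair of visits equally correlated, and every visit equally variable. The fitted correlation is then a compromise over all pairs. If the month 0-month 12 pair is less correlated than that compromise, the model understates the variance of the change from 0 to 12, which is the primary contrast.

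The documents give reasons to expect a weaker link to month 0:

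- Protocol Table 1 has SIS collected in hospital by site staff before discharge. The follow-up assessments come from the survey unit, whose telephone interviewers are blinded (Protocol 10).
- SAP 3.3 says that the baseline was the 96-item long form, from which 16 items are extracted. Follow-up uses the 16-item form.
- Months 0 and 12 are the two visits furthest apart.
- With about half of month 0 missing, pairs of follow-up visits weigh more in the pooled correlation.

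At stake are the p-value and confidence interval of one of the two primary outcomes. This is a patient-level matter and would arise even with no site variation.

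**Working it through.** **The plan's own figures.** The documents state no error rate for the change contrast. The power figures in Protocol 9.A do reproduce. With SD 8, 900 per arm, 100 per site and ICC 0.05, SE = 8 × √(2 × [1 + 99 × 0.05]/900) = 0.920. A t-test with 16 df then detects 2.75 (80% power) and 3.18 (90%), against the stated 2.7 and 3.2. With ICC 0.10, SE = 1.245 and the results are 3.72 and 4.30, against 3.7 and 4.3. These figures concern a mean difference with no between-visit correlation in it, so they do not bear on this question.

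**Formula, complete data and equal SDs.** Let ρ₀,₁₂ be the true correlation of months 0 and 12, and ρ̄ the average over the six visit pairs, which is what the random-intercept model estimates.

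- True variance of a patient's change: 2σ²(1 − ρ₀,₁₂).
- Variance under the model: 2σ²(1 − ρ̄).
- SE ratio, model to true: k = √[(1 − ρ̄)/(1 − ρ₀,₁₂)].
- Type I error at nominal two-sided 5% (assumed from the SAP's 95% intervals): 2Φ(−1.96k).

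σ and the number of patients cancel, and so does a site effect that is constant over visits.

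*Month 0 with follow-up 0.5, follow-up visits with each other 0.8:* ρ̄ = (3 × 0.5 + 3 × 0.8)/6 = 0.65; k = √(0.35/0.50) = 0.837; 1.96k = 1.640; type I error 10.1%.

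*0.6 and 0.7:* ρ̄ = 0.65; k = √(0.35/0.40) = 0.935; 1.96k = 1.833; type I error 6.7%.

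**Half of month 0 missing.** No simple formula applies. The two parameters of the equal-correlation model were set to the values that best fit the assumed true covariance over the missing-data patterns. The model-based variance of the contrast was then compared with its true (sandwich) variance. All correlations are assumptions.

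| Assumed pattern, equal SDs | Month 0 complete | Month 0 half missing |
|---|---|---|
| Equal, 0.6 or 0.8 | 5.0% | 5.0% |
| Month 0 0.6, follow-up 0.7 | 6.7% | 8.0% |
| Month 0 0.5, follow-up 0.7 | 8.0% | 10.5% |
| Month 0 0.6, follow-up 0.8 | 9.0% | 12.8% |
| Month 0 0.5, follow-up 0.8 | 10.1% | 15.2% |
| Month 0 0.4, follow-up 0.8 | 11.0% | 17.1% |
| AR(1) by visit, 0.5 to 0.9 | 9.2-13.4% | 8.7-13.1% |

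The missing baseline makes matters worse when month 0 stands apart from the other visits. Under AR(1) decay it makes little difference.

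**Unequal SDs.**

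- Equal correlation 0.6, month-0 SD 0.7 times follow-up: 3.8% (complete) and 2.5% (half missing). With month-0 SD 1.3 times: 7.0% and 9.6%.
- With half of month 0 and an assumed 15% of later visits missing, the 0.6/0.7 pattern gives 7.5% with equal SDs and 5.5% with month-0 SD 20% smaller. Equal correlation with that smaller SD gives 3.2%.
- The 0.5/0.8 pattern with half of month 0 missing gives 11.8% at month-0 SD 0.7 times follow-up and 19.4% at 1.3 times.

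**Month-12 level alone.** In the equal-SD patterns the type I error stays at about 5-6%.

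**Simulation check.** REML fits, 21 sites of 60 patients, 300 runs, rates for complete and half-missing month 0. Equal correlation 0.6: 5.3% and 4.0%. AR(1) 0.8: 10.3% and 10.7%, against 12.4% and 12.0% by calculation (Monte Carlo error 1-2 points).

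**The case against.** The strongest reply is that the SAP does not say a random intercept is the whole within-patient model. It lists repeated measures as a separate item, and in the SAS family that can mean a residual covariance, even an unstructured one. The sentence is qualified as a general approach, is written for binary factors at three visits, and reaches SIS only by cross-reference. This stands: the random-intercept model is one reading. It is a natural reading, since a patient intercept on top of an unstructured residual would be redundant. On any other reading, the primary p-value still depends on an unstated choice.

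The second reply is that the size rests on assumed correlations, and that the SD could work the other way. Everyone is alive at discharge, and Protocol 9 gives a floor score to patients who die or cannot return. That could widen the follow-up SD relative to month 0 and shrink or reverse the inflation. This also stands, and it is why the range starts below 5%.

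A reader might also infer that a wrong correlation spoils the handling of the missing baseline SIS in general. The documents do not support that. SAP 3.3 attributes the gap to a decision taken about halfway through recruitment. If that is unrelated to outcome, a misspecified correlation affects efficiency and the model-based standard errors but does not bias the visit means.

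**Conclusion.** The point holds conditionally. SAP 3.3 leaves the within-patient covariance for its primary SIS contrast unspecified apart from a patient random effect. If a random intercept alone is fitted, the nominal 5% test of change has a type I error of:

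- about 5% if all visits are equally correlated with equal SDs;
- about 5-8% under mild inequality (0.6 against 0.7, month-0 SD equal or 20% smaller);
- about 9-17% if the discharge correlation is clearly weaker, with equal SDs;
- below 5% if correlations are equal and the month-0 SD is smaller.

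It is tempting to say that the plan has a false-positive rate of 9-17%. The documents do not support that, because they give no SIS correlations or SDs by visit and do not exclude a residual covariance. They do make equal correlation implausible, for the reasons of setting, assessor, form and interval given above. The month-12 comparison is essentially unaffected, and nothing is claimed for mRS, which was not computed.

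**What to change.** In SAP 3.3, state that SIS at months 0, 3, 6 and 12 is modelled with an unstructured 4x4 within-patient covariance (in SAS, REPEATED visit / SUBJECT=patient TYPE=UN) in place of the patient random intercept, keeping the site random effect. With the patient covariance modelled correctly, the model and true standard errors agree, and the error from this source returns to 5% whatever the correlations are.

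The cost is one sentence in the SAP, 10 covariance parameters instead of 2 (readily estimated from about 1,262 patients), and probably a wider interval.

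This corrects only the patient-level source. A site effect that is constant over visits largely cancels from a change contrast, so variation between sites in their change over time is not covered. In the limited simulations, all with patient and site random intercepts, an assumed site-by-visit variance of 2% of the total raised the type I error to about 29-37%. That needs its own provision in the SAP; a reader should not take the unstructured covariance alone as making the interval correct.

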- (1) The ISPU approach will improve secondary stroke outcomes relative to the CSC/PSC approach, including: SIS and smRS at 3 and 6 months, risk factor control, stroke recurrence rates, hospital readmission rates, mortality in the first 12 months, time at home, patient depression, and caregiver strain.
- (2) The ISPU benefit in SIS and smRS will persist after the protocol-based post-acute coordination of in-home/facility care is terminated (at 12 months).
- (3) Patient characteristics (specifically age, race, sex, income, and education) will affect the primary or secondary intervention differences.

B. Primary and Secondary Outcomes

Primary and secondary outcomes are documented in Table 1 and described below.

- *Primary outcomes* include patient function and QOL using the SIS and smRS at 12-months post-stroke.
- *Secondary outcomes* are patient/caregiver-centered and include: (1) short-term patient function and QOL using the SIS and smRS (at 3 and 6 months); (2) the proportion of patient with risk factors controlled at target (at 3, 6, and 12 months); (3) mortality in the first 12 months, time to first recurrent stroke, and number of hospital readmissions per participant month over the first 12 months; (4) Time At Home (proportion of survival time spent at home); (5) patient depression, using the Patient Health Questionnaire (PHQ-9; at 3, 6, and 12 months); and (6) caregiver strain, using the Caregiver Strain Index (CSI; at 3, 6, and 12 months).

Table 1. Study Outcome Measures and Assessment Frequency					
C3FIT OUTCOMES	VARIABLES	ASSESSMENT FREQUENCY (By Month)			
		H	3	6	12
Functional Assessment	Stroke Impact Scale	X	X ⁺	X ⁺	X ⁺
Quality of Life	Simplified Modified Rankin Scale	X	X ⁺	X ⁺	X ⁺
Stroke Risk Factors					
(1) Blood pressure control at target*	Standard Systolic and Diastolic Measurement	X	X	X	X
(2) Lipid control at target*	Standard Lipid Panel or, at a minimum, LDL (Blood Draw, repeated only if patient's cholesterol is elevated at baseline, if LDLC%≥70mg/dl, or if patient is on a statin)	X	X	X	X
(3) Diabetes control at target*	Standard HBA1c (Blood Draw, repeated only if patient's blood glucose is elevated at baseline or if HBA1C%≥7mg/dl)	X	X	X	X
(4) Smoking status*	Question(s) to assess patient smoking status	X	X	X	X
(5) Body Mass Index (BMI)*	Weight and hip circumference	X	X	X	X
(6) Diet	Question(s) to assess patient adherence to recommendations of the American Heart Association (AHA).	X	X ⁺	X ⁺	X ⁺

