6. BASELINE AND FOLLOW-UP ASSESSMENTS AND LABORATORY EVALUATIONS

The following outlines the Data Paradigms for the CSC/PSC arm based on obtained values for various scales and data points utilized. The guidelines establishing blood pressure and cholesterol goals are from the American Heart and Stroke Association.⁸

A. On-Study/On-Intervention Evaluations

The schedule of evaluations occurring after randomization while the subject is on-study and on (or about to start) intervention along with allowable time window in which evaluations may take place (± 30 days with a target of ± 14 days) is shown in Table 7. Primary and secondary outcomes are considered a mandatory part of the protocol; remaining measures will be collected if patient/caregiver are able and/or available.

Table 7. Data Collection Paradigm: CSC/PSC Arm

Item/Metric	In Hospital Prior to Discharge	Post Discharge Visit												
		Day 0-14	Month of Visit to Home/Facility											
			1	2	3	4	5	6	7	8	9	10	11	12
Informed Consent Confirmed	X			X			X						X	
Demographics (Age, Gender, Race/Ethnicity, Marital Status, Zip Code of Residence, Income, and Education)*	X			X			X						X	
Caregiver/Family identified*	X			X			X						X	
Medical Record Number (MR #)*	X													
Get-With-The-Guidelines (GWTG) in-hospital data*	X													
Complications* ¹	X			X			X						X	
Patient Medical History	X			X			X						X	
National Institutes of Health Stroke Scale (NIHSS)*	X												X	
Stroke Subtype*	X													
Prior stroke/Transient Ischemic Attack (TIA)*	X													
Risk factor profile* ²	X												X	
Cholesterol panel or LDL*	X			X			X						X	
Hemoglobin A1C (HBA1C)*	X			X			X						X	
Perceived Support				SRU			SRU						SRU	

Stroke Impact Scale (SIS)				SRU			SRU						SRU
Simplified Modified Rankin Scale (smRS)	X			SRU			SRU						SRU
Blood Pressure (BP) Control: at target	X			X			X						X
Lipid Control: LDL, at target	X			X			X						X
Diabetes Control: HBA1C, at target	X			X			X						X
Smoking Status	X			X			X						X
Body Mass Index (BMI)	X			X			X						X
Diet Assessment	X			SRU			SRU						SRU
Exercise Assessment	X			SRU			SRU						SRU
Mortality surveillance				X			X						X
Recurrence surveillance				X			X						X
Readmission surveillance				X			X						X
Time at Home				X			X						X
Depression: Patient Health Questionnaire (PHQ-9)				X			X						X
Caregiver Strain Index (CSI)				X			X						X

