In addition to this primary analysis of the intermediate factors that is restricted to those not compliant/adherent at discharge, a supplemental analysis will assess the proportion compliant at 3, 6, and 12 months regardless of compliance at month 0 (i.e., proportion compliant/adherent in the entire population). This analysis will consider a mixed modeling approach with outcomes at 4 time points (0, 3, 6, and 12 months). The focus of this analysis will be on the change in the proportion compliant between month 0 and 12 months (but also reporting the change in the proportion to 3 and 6 months). In addition to assessing treatment differences in the change in the proportion, the treatment differences in the proportions at the 4 time points will be assessed.

For all six factors, analyses assessing the potential for bias from missingness will be performed using inverse probability weighting (for both the analysis restricted to those not compliant/adherent and for the entire population analysis). This will be conducted by first developing a logistic regression model estimated in all subjects predicting the probability of observing the 12-month observation. Predictors in the model will be site (with cluster randomization, implicitly including treatment effect), age, NHW race/ethnicity, sex, NIHSS and nSES. The inverse of this probability will be standardized by dividing by the sum of the inverses, standardizing the inverse probabilities to have the same sum as the sample size; hence, not inflating or deflating statistical power. The analysis for the factor will then be repeated using the inverse probability weights. Should the interpretation of results differ between the weighted and unweighted analyses, the primary interpretation will be based on the weighted analysis, and the weighted analysis will be the basis for figures and estimates in the manuscript will focus on the weighted results.

Effect modification will be assessed by age, sex, race/ethnicity, stroke sub-type, stroke severity (discharge NIHSS dichotomized at 0 to 1 versus 2+), and nSES.

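### Protocol Tables 1 and 7 conflict on repeat HbA1c and LDL tests; if Table 1 was applied, the whole-population analysis in SAP 3.1 rests on an untestable assumption about patients already in control

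*SAP*

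**What the plan says.** **SAP 3.1 (intermediate factors).** The main analysis of each factor is confined to patients out of control at discharge (for example HbA1c of 7% or above, LDL of 70 mg/dL or above). The reason given is "Because the ISPU intervention was targeted to specific groups determined by baseline assessments". The SAP then adds that "a supplemental analysis will assess the proportion compliant at 3, 6, and 12 months regardless of compliance at month 0", for all six factors, using a mixed model with four time points. "The focus of this analysis will be on the change in the proportion compliant between month 0 and 12 months", and arm differences at each time point are also reported. An inverse-probability-weighted repeat is planned. If its interpretation differs from the unweighted one, the weighted result takes precedence.

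**Protocol Table 1 (section 1.B, same rule in the ISPU and CSC/PSC versions).** HbA1c is marked at hospital, 3, 6 and 12 months, but the draw is "repeated only if patient's blood glucose is elevated at baseline or if HBA1C%≥7mg/dl". The LDL draw is "repeated only if patient's cholesterol is elevated at baseline, if LDLC%≥70mg/dl, or if patient is on a statin".

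**Protocol Table 7 (section 6.A, both versions).** The laboratory rows and the control rows, such as "Diabetes Control: HBA1C, at target", are marked at hospital and at 3, 6 and 12 months, with no re-test condition.

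The SAP does not mention the Table 1 rule and does not say how an untested patient is counted.

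**The concern.** The Table 1 triggers of 7 for HbA1c and 70 for LDL are also the SAP's limits for being in control. If that rule was followed, the baseline value of the outcome largely decides who is measured again. Month 0 would include the patients in control at discharge, while months 3 to 12 would contain only those who carry another flag: elevated glucose for HbA1c, elevated cholesterol or a statin for LDL.

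The model would then have to supply month-12 status for unflagged controlled patients from its fitted form and from other patients' data. SAP 3.1 itself gives a reason to doubt that step, since it describes the intervention as directed at groups defined by baseline status.

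This matters beyond a sensitivity table. The protocol lists the proportion of patients with risk factors at target as a secondary outcome, and this is the only SAP analysis that estimates it in all patients. SAP section 1 also calls the intermediate factors an integral part of the primary assessment. A true gain or loss in keeping controlled patients in control could go unseen.

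**Working it through.** The documents give no rate, power or sample size for this analysis, so there is no stated figure to reproduce. All rates below are assumptions.

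**Notation (HbA1c).** p0 = share in control at month 0. g = share of those re-tested because of glucose. a = probability that an out-of-control patient is in control at month 12. b = probability that a controlled patient stays in control. Subscripts I and C denote ISPU and CSC/PSC.

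**Step 1: what the data can see.**
- True month-12 proportion in an arm = p0·b + (1 − p0)·a.
- With p0 equal in both arms, the true arm difference (at month 12 and in the change) = p0·(bI − bC) + (1 − p0)·(aI − aC).
- If g = 0, a controlled patient contributes only the month-0 value to the likelihood, so b never enters the fit and the first term is invisible. At p0 = 70%, each point of arm difference in retention moves the truth by 0.7 points and the estimate by nothing.
- If g > 0, a share p0·(1 − g) of all patients is still unobserved: 63% at g = 10% and 49% at g = 30%.

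**Step 2: fitted model against truth.** Inputs: p0 = 70%, aI = 50%, aC = 40%, g = 0. A random-intercept logistic model (arm by four visits, 1,262 patients, site omitted, latent correlation 0.8 among follow-up visits, mean of 12 simulated data sets) was fitted to data deleted by the Table 1 rule. True values come from the formulas above; the simulated sets average within about 1.2 points of them.

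| Stay in control, I / C | True CSC/PSC change | Fitted change | True arm difference | Fitted arm difference |
|---|---|---|---|---|
| 99% / 99% | +11.3 | +9.6 | 3.0 | 3.1 |
| 95% / 95% | +8.5 | +9.6 | 3.0 | 3.1 |
| 80% / 80% | −2.0 | +9.6 | 3.0 | 3.1 |
| 95% / 85% | +1.5 | +9.6 | 10.0 | 3.1 |

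Worked last row: 0.70 × (0.95 − 0.85) + 0.30 × (0.50 − 0.40) = 0.07 + 0.03 = 0.10. The fitted columns do not move, as Step 1 requires.

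**Step 3: effect of the glucose clause.** For the last row, the fitted difference rises to 4.0 at g = 10% and 6.9 at g = 30%, against a truth of 10.0. A repeat with 400,000 simulated patients gave 5.7 and 7.7 for the arm difference in change. These values are therefore approximate, but all fall short of the truth.

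**Step 4: dependence on the model.** With 95% retention in both arms and g = 0 the truth stays at 3.0. In the larger repeat the fitted arm difference in change was 9.1, 6.5 and 4.0 points at follow-up correlations of 0.3, 0.5 and 0.7, and between 3 and 4 at 0.8 and 0.9. The agreement in the second row of the table therefore depends on the assumed correlation.

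**Step 5: can the SAP's other tools repair it?**
- *Weights.* The observation model uses site, age, race/ethnicity, sex, NIHSS and nSES. It contains no HbA1c, glucose, LDL or statin term. Adding them would not help: an unflagged controlled patient has zero probability of a month-12 value, so no observed patient can stand in for that group.
- *Covariates.* SAP section 2 removes covariates directly related to the outcome. On that rule diabetes would leave the HbA1c model and dyslipidemia the LDL model.

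**Step 6: LDL.** Share of all patients not re-tested = P(LDL below 70) × (1 − share of those with a statin or cholesterol flag). Assuming 20% to 50% below 70, and 42% to 90% of them flagged, this runs from 0.20 × 0.10 = 2% to 0.50 × 0.58 = 29%. No LDL bias was computed.

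**The case against.** **The premise is open.** Table 7 is the visit schedule, and it marks both tests unconditionally in both arms. Its control-at-target rows carry no if-available footnote, and section 6.A calls primary and secondary outcomes mandatory. Section 10.A also describes the blood draws by schedule, with no re-test condition. If Table 7 was followed, only the conflict between the tables remains. This stands, and the point is conditional for that reason. Nor can one say that month 0 is measured in everyone, because the laboratory rows themselves are footnoted as collected if the patient or caregiver is able or available.

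**A mixed model can handle such missingness.** If re-testing depends only on the month-0 value, the data are missing at random given that value, and the fit can land close to the truth, as in the 95% / 95% row. This also stands. But the result then holds because of the model's form, which nothing observed in unflagged controlled patients can test.

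**Stronger readings a reader might infer.**
- That the unweighted estimate is already wrong, or about twice the truth. Some assumed data models do give a ratio near two; the one in Step 2 gives 3.1 against 3.0. The documents supply no rate to choose between them.
- That the report would show a large fall in control. Among re-tested patients only, the CSC/PSC proportion would go from 70% to 40% with g = 0, an apparent change of −30 points against a true +8.5. That comparison is not the planned estimate, because the SAP's model includes month 0.
- That LDL is affected as much as HbA1c. The statin clause may leave few patients untested, and the documents give no statin rate for this trial.

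**Conclusion.** The point holds in conditional form. Tables 1 and 7 contradict each other on repeat HbA1c and LDL tests and must be reconciled. If Table 1 was applied, the whole-population HbA1c change and arm difference in SAP 3.1 rest on an untestable assumption about unflagged controlled patients, and the planned weights cannot remove it. For LDL the same holds to a smaller and unquantified extent.

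Size and direction depend on assumed rates. The error in the arm difference can be near zero when retention is high and equal between arms. It is about 7 points (3.1 fitted, 10.0 true) when retention is 95% against 85%, 70% are in control at month 0 and none of them is re-tested. Re-testing for elevated glucose narrows the gap.

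A reader might infer that the trial's main conclusions are at risk. The documents do not support that. The main intermediate-factor analysis uses patients at or above the cut-off, all of whom Table 1 re-tests, and the mRS and SIS do not depend on these draws. The affected analysis is labelled supplemental.

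**What to change.** 1. State in SAP 3.1 which schedule the sites applied for repeat HbA1c and LDL, and correct the other protocol table in both arm versions.
2. Report, by arm and visit, the number tested according to control status at discharge.
3. If Table 1 applied: limit the HbA1c and LDL version of this analysis to patients eligible for re-test, at all four time points, and label it as such. Give any whole-population figure only as a sensitivity range over stated retention assumptions for untested patients, set separately in each arm.
4. If Table 7 applied: correct Table 1 and keep the analysis as planned.

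Cost: one table correction, a short SAP addition and one table of counts. The downside, if Table 1 applied, is that the whole-population HbA1c and LDL results become narrower in scope or appear only as a range.
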